6.4.2 Analysis of Key Secondary Efficacy Endpoints

The population used for the analysis of key secondary endpoints will be the ITT population. Adolescent and moderate/severe renally impaired participants that are enrolled directly into the WL/NIR-F arm will not be included in the analysis of the key secondary endpoints.

The first key secondary endpoint of the 30-min time point WL conspicuity score versus the mean NIR-F conspicuity score across all time points will be analyzed using a sign test which will test if the median of the intra-participant time point difference means between the NIR-F score at each time point and the 30-min WL score is equal to 0. Prior to the analysis, the conspicuity scores will be windowed to time points every 30 minutes per the algorithm in Section 6.8.1.

The value used in the sign test for each participant will be derived as follows. The differences between the NIR-F scores at each time point and the 30-min WL score will be calculated for each participant. The mean of these differences will then be calculated for each participant. A sign test will be conducted using these mean differences to test if the median of the intra-

participant time point difference means between the NIR-F scores and 30-min WL scores is equal to 0.

Prior to the sign test, participants who experience ICE1 or ICE2 will have their 30-min conspicuity data imputed using the same algorithm as described in section [6.4.1.1](#).

Additionally, the following imputation rules will be applied to NIR-F conspicuity scores at other time points after 30-min prior to the sign test.

- Participants who experience ICE1 will have NIR-F conspicuity scores at time points after ICE1 set as their WL conspicuity assessment at the 30-min time point.
- Participants who are unable to have NIR-F conspicuity scores assessed by the investigator at time points after 30-min will have such NIR-F scores left as missing.

If a participant does not have a conspicuity assessment at a time point due to the surgery ending before the time point, the time point will be left as missing prior to the sign test.

The following results will be presented:

- For comparisons between WL and NIR-F:
 - Frequency and percentage of participants with a positive mean difference, negative mean difference and mean difference of 0.
 - Summary statistics of the mean differences between 30-min WL and NIR-F time points.

The mean differences will be used to obtain a 2-sided p-value to test if the median of the mean differences is equal to 0.

[figure not shown]
The second key secondary endpoint of the 30-min time point WL conspicuity score vs the end of surgery NIR-F conspicuity score will be analyzed using a paired t-test.

Descriptive statistics will be used to summarize the ureter conspicuity at the 30-min time point with WL and the end of surgery (EoS) time point with NIR-F. The same imputation algorithm described in the analysis of the first key secondary endpoint will be applied to the data prior to setting the EoS NIR-F value for each participant. Descriptive statistics for the differences between the ureter conspicuity scores and 95% 2-sided confidence interval for the mean difference and p-value will be presented.

A fixed sequence testing procedure will be used to adjust for multiplicity and control the type I error rate. The hypothesis tests will be conducted in the following order.

- H1: WL conspicuity at 30 minutes vs NIR-F conspicuity at 30 minutes
- H2: WL conspicuity at 30 minutes vs mean NIR-F conspicuity across all time points
- H3: WL conspicuity at 30 minutes vs NIR-F conspicuity at end of surgery

H2 will only be tested if the H1 p-value is ≤ 0.05 . H3 will only be tested if both the H1 and H2 p-values are ≤ 0.05 . A graphical representation of the testing procedure is given below.

The values within the circles indicate the initial allocation of the 0.05 significance level. Therefore, at the initial test, the primary endpoint (H1) will be tested at the full significance level of 0.05 and the key secondary endpoints will not be tested. The values on the lines indicate the significance level from the prior step that is allocated to the next step if the null hypothesis is rejected. Therefore, if the null hypothesis for the primary endpoint is rejected, the first key secondary endpoint (H2) will be tested at the full significance level of 0.05. Subsequently, if the null hypothesis for the first key secondary endpoint is rejected, the second key secondary endpoint (H3) will be tested at the full significance level of 0.05.

6.4.3 Analysis of Secondary Efficacy Endpoints

The secondary efficacy endpoints are listed in section 5.3. The analysis of additional secondary endpoints including CEF data will be conducted using all participants in the mITT population. CEF data will be mapped to time points using the windowing algorithm described in Section 6.8.1.

Quantitative assessment of ureter conspicuity will be performed by image analysis using recorded images. CEF is a measure of the degree to which color contrast is enhanced in area in which ASP5354 fluorescence signal is present when compared to areas in which ASP5354 fluorescence signal is absent. The CEF value is utilized as a quantitative analog for the qualitative assessment of “conspicuity” by the surgeon. An independent vendor will perform the image analysis using WL and NIR-F images extracted from the video files for all time points specified in the protocol schedule of events. A separate study image analysis charter/plan will describe details of the image analysis methodology and image analysis processes. The contrast enhancement factor (CEF) is derived by first normalizing the green signal to remaining colors (red and blue) for the same area as of the tissue within the WL and NIR-F images. The WL and NIR-F color contrasts are then calculated as a ratio of this normalized green signal inside and outside of the ureter. The CEF value is then calculated by taking the NIR-F color contrast and dividing by the WL color contrast.

WL and NIR-F color contrast values and CEF values will be summarized using descriptive statistics by time point.

The overall Pearson correlation coefficient between the WL color contrast values and WL conspicuity scores as well as the NIR-F color contrast values and NIR-F conspicuity scores will be presented.

In the event that WL or NIR-F images are reviewed and the ureter is unable to be located by the CEF reader, the color contrast for that image will be imputed as 1 for the analysis. Images which are collected after a patient experiences ICE1 will have the color contrast imputed as 1 for the analysis.

CEF data will be listed.

Boxplots for the distribution of WL and NIR-F CEF values for the index and non-index ureters will be presented. Boxplots for the distribution of CEF values by conspicuity score for the index and non-index ureters will be presented.

The analysis of the additional secondary endpoints will be conducted using the following groups of participants. P-values and confidence intervals will not be presented. This analysis will be performed after applying the ICE1 and ICE2 imputation as well as the visit windowing algorithm described in section [6.8.1](#).

- Adolescents
- Adults with moderate renal impairment (eGFR ≥ 30 to < 60 mL/min)
- Adults with severe renal impairment (eGFR ≥ 15 to < 30 mL/min)

To further characterize the difference of ureter conspicuity under NIR-F vs WL, the frequency and percentage of participants with an averaged ureter conspicuity assessed by the investigator over all NIR-F time points during surgery at least 1 point higher than the average ureter conspicuity over all WL time points during surgery will be presented. The same analysis will be repeated using a difference of 2, 3 and 4 points. The frequency and percentage of participants with an averaged ureter conspicuity within NIR-F during surgery at least 1 point higher than their WL conspicuity at the 30-min time point during surgery will be presented. The analysis will also be repeated using a difference of at least 2, 3 and 4 points.

The qualitative assessment of index ureter(s) conspicuity scored on a 5-point Likert Scale under WL and NIR-F (1 = None, 2 = Poor, 3 = Sufficient, 4 = Good and 5 = Excellent) performed by a BICR will be summarized descriptively at all time points post-ASP5354 administration by WL and NIR-F for each separate BICR reader. The descriptive analysis of the primary and key secondary endpoints will be repeated for each separate BICR reader. This analysis will be conducted within adolescents, adults with moderate renal impairment, adults with severe renal impairment, the ITT population and the mITT population. The BICR data will be assigned to the same analysis time points as the corresponding investigator assessments. The same ICE1 and ICE2 imputation will also be applied within the BICR data. In the event that a BICR assessment cannot be collected for a corresponding investigator assessment, the corresponding analysis time point will be considered missing in the BICR analysis. If a backup reader is utilized in place of a primary reader, the primary reader and their backup will be considered the same BICR reader in the analysis.

The concordance analysis between BICR readers and investigators will be conducted for the ITT population. The hypothesis testing for the primary and key secondary endpoints will be repeated for each separate BICR reader. This will be the primary measure of concordance between the BICR readers and investigator data. A high concordance between the two assessments is considered if 2 of 3 BICR readers yield p-value ≤ 0.05 .

The CCC measuring the agreement between investigator and BICR Likert conspicuity scores will be presented for the following values for each separate BICR reader for the ITT population. This is considered a secondary measure of reliability compared to the hypothesis testing as differences between the raw conspicuity scores of the BICR readers and investigator data may be expected due to the different environments under which conspicuity is assessed.

- Difference between NIR-F and WL at the 30-min time point
- Mean difference between NIR-F across all time points and WL at the 30-min time point
- Difference between NIR-F at the end of surgery time point and WL at the 30-min time point

In addition to the CCC, Kendall's coefficient of concordance along with 95% jackknife CI will be presented in order to assess the agreement across all raters.

BICR data will be listed.

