#### 7.1.2 Adults with Normal/Mild eGFR

Each site with adult participants will designate an unblinded study member who will randomize participants via the study’s IRT system. Investigators will be blinded to the randomization assignment until after completion of the first ureter conspicuity assessment (by the study-specific 5-Point Likert Scale; hereafter, referred to as the 5-Point Likert Scale) performed for ureter(s) of interest with WL at 30-min after ASP5354 administration. This first WL assessment will be done when the investigator reaches the point in the surgery that visualization/identification of the ureter(s) is required.

If the first assessment timeframe is missed (30 [ $\pm$  15] min post-ASP5354 administration), the first conspicuity assessment for the study must be done while investigators remain blinded to

the participant's randomization assignment. The time of the conspicuity assessment will be recorded at all time points. Following this assessment, the unblinded study member will provide the investigator with the randomization assignment of the participant. If the participant was randomized to the:

- WL/NIR-F arm: the 30-min time point ureter conspicuity assessment will also be performed with NIR-F for the investigator-selected ureter(s) of interest (i.e., right, left or both). Thereafter, the investigator will assess the conspicuity of selected ureter(s) with WL and with NIR-F every 30 ( $\pm$  15) min for the duration of the surgery, with the last assessment performed at the end of surgery time point.  
Note: The end of surgery time point is defined as the last time point where the ureter can be captured in the surgical field before removal of laparoscopic instruments or before the beginning of closure of the abdomen for open surgeries. If a surgical approach is switched from laparoscopic to open during surgery, ureter conspicuity assessment must be performed until the end of the laparoscopic surgery part and can be continued until the end of the open surgery part at the investigator's discretion. The actual end of surgery is defined as the moment when all the procedures related to the surgery/surgery part that the investigator planned for the study are concluded.
- WL-only arm: only the 30-min time point after ASP5354 administration ureter conspicuity assessment will be performed with WL for the ureter(s) of interest (i.e., right, left or both).  

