		6.1	text added	to clarify which BICR assessment will be analyzed when there are multiple readings of an image
		6.2.3	age categories updated	to summarize the 12-14 and 15 to 17 age groups
		6.2.3, 6.4.5	text added	added summaries for type of device
		6.2.3, 6.5.1.1, 6.5.1.2, 9.3	text updated	specific MedDRA version removed
		6.4.1.2	text added	added sensitivity analysis excluding participants who do not receive study drug

SAP Version	Approval Date	SAP Section(s)	Change	Rationale
		6.4.3	text updated	clarified inter and intra-rater reliability will be analyzed for BICR readers
		6.4.3	text updated	clarified that the Pearson correlation coefficient will be displayed only for the overall data in the CEF analysis and not for each time point
		6.4.3	text added	Kendall's W statistic added to analysis
		6.4.3	text added	clarification added regarding instances where a BICR assessment cannot be collected
		6.4.3, 6.4.5	text added	added text for figures that will be presented
		6.4.5	text added	added new analysis for categorical summary of conspicuity scores and accidental unblinding listing, clarified that certain summaries of conspicuity data will not implement ICE1 or ICE2 imputation
		6.4.5	text added	added table and listing for ICEs
		6.4.5	text added	added table and listing for ICEs
		6.4.5	text added	clarified which efficacy analyses will have data imputation applied
		6.6	text added	added clarification for urine volume calculation

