5.3 Secondary Efficacy Endpoints

The other secondary efficacy endpoints are as follows:

- Using recorded images, ureter conspicuity for WL and NIR-F illumination modes will be quantified by image analysis of all time points for all participants in mITT population

- Descriptive summary of intra-participant differences in ureter conspicuity for WL versus NIR-F at the 30-min time point after ASP5354 administration for adolescents
- Descriptive summary of ureter conspicuity scores for WL at the 30-min time point versus the average of all NIR-F time points for adolescents
- Descriptive summary of ureter conspicuity scores for the WL 30-min time point versus the end of surgery time point score with NIR-F for adolescents
- Descriptive summary of intra-participant differences in ureter conspicuity for WL versus NIR-F at the 30-min time point after ASP5354 administration for adults with moderate or severe renal impairment
- Descriptive summary of ureter conspicuity scores for WL at the 30-min time point versus the average of all NIR-F time points for adults with moderate or severe renal impairment
- Descriptive summary of ureter conspicuity scores for the WL 30-min time point versus the end of surgery time point score with NIR-F for adults with moderate or severe renal impairment
- Descriptive summary of intra-participant differences in ureter conspicuity for WL versus NIR-F at the 30-min time point after ASP5354 administration for participants in the mITT population
- Descriptive summary of ureter conspicuity scores for WL at the 30-min time point versus the average of all NIR-F time points for participants in the mITT population
- Descriptive summary of ureter conspicuity scores for the WL 30-min time point versus the end of surgery time point score with NIR-F for participants in the mITT population
- Frequency and percentage of participants with an average index ureter conspicuity over all NIR-F time points at least 1 point higher than the average index ureter conspicuity over all WL time points
- Frequency and percentage of participants with an average index ureter conspicuity over all NIR-F time points at least 2, 3 or 4 points higher than the average index ureter conspicuity over all WL time points
- Intra-participant difference in ureter conspicuity assessed by BICR for WL versus NIR-F at 30 (± 15) min after ASP5354 administration for all participants in the ITT population

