6 STATISTICAL METHODOLOGY

6.1 General Considerations

Continuous data will be summarized descriptively including the number of participants (n), mean, standard deviation (SD), median, minimum and maximum. In addition, for continuous PK variables and PK parameters, coefficient of variation (%CV), geometric mean (GM) and geometric coefficient of variation (Geo %CV) will also be calculated. GM and Geo %CV will not be calculated if at least one value is below the quantification limit (BQL).

Categorical data will be summarized by frequencies and percentages. Percentages by categories will be based on the number of participants with no missing data, i.e. the

percentages for the non-missing categories will add up to 100%. All non-coded free-text variables will be displayed in data listings only.

All statistical comparisons will be conducted using 2-sided tests at the 5% significance level unless stated otherwise.

All data summarization and analyses will be performed using SAS® Version 9.4 or higher on Red Hat Enterprise Linux. Specifications for table, figures, and data listing formats can be found in the TLF specifications document for this study.

Baseline for the safety and tolerability analysis is the last measurement taken prior to ASP5354 administration.

Efficacy summaries for the primary and key secondary endpoints will be presented for all participants in the ITT population which includes all participants in the adult normal/mild eGFR cohort randomized to WL/NIR-F. Efficacy data collected for adult participants randomized to the WL-only arm will be listed only. Efficacy summaries for the adolescent and adult moderate/severe eGFR cohort will be presented as other secondary analyses. Efficacy analyses will be presented for all participants in the mITT population as other secondary analyses.

Unless otherwise specified, efficacy analyses will use data from one ureter for each participant based on selection by the investigator. If the investigator selects either the left or right ureter as the ureter of interest before surgery, then data from the selected ureter will be used in the efficacy analyses. If the investigator selects both ureters as ureters of interest, the index ureter selected by the investigator (either left or right) will be used in the efficacy analyses.

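### The overall Pearson coefficient of color contrast against conspicuity score pools repeated time points, so it cannot show whether contrast tracks the score within a participant

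*SAP*

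**What the plan says.** The image measure is an additional secondary endpoint: conspicuity "will be quantified by image analysis of all time points for all participants in mITT population" (SAP 5.3). Protocol 9.3.3.2 promises to examine its correlation with the investigator's scores and leaves the details to the SAP. SAP 6.4.3 supplies them: "The overall Pearson correlation coefficient between the WL color contrast values and WL conspicuity scores as well as the NIR-F color contrast values and NIR-F" scores are to be correlated overall, giving two coefficients, one for white light and one for NIR-F.

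Read alone, the word overall could be taken in more than one way. The SAP version history (version 4.0, entry for 6.4.3) makes the meaning plain: it "clarified that the Pearson correlation coefficient will be displayed only for the overall data in the CEF analysis and not for each time point".

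Both members of each pair are repeated measures:

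- Scores: after the 30-min assessment, "the investigator will assess the conspicuity of selected ureter(s) with WL and with NIR-F every 30" minutes until the end of surgery (Protocol 7.1.2 and Table 2).
- Images: "An independent vendor will perform the image analysis using WL and NIR-F images extracted from the video files for all time points specified" in the schedule (SAP 6.4.3).
- Analysis set: "The analysis of additional secondary endpoints including CEF data will be conducted using all participants in the mITT population" (SAP 6.4.3), which covers all cohorts evaluated with both modes.
- Ureters: "Unless otherwise specified, efficacy analyses will use data from one ureter for each participant based on selection by the investigator" (SAP 6.1), so there is no second layer of clustering by ureter.

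Neither document mentions averaging by participant, weighting, or a repeated-measures correlation for this analysis.

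**The concern.** The measurement unit is a time point nested in a participant. A coefficient computed over all pairs gives a participant with many time points more weight than one with a single time point. It also mixes two different questions:

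- Do participants with higher contrast tend to receive higher scores?
- When contrast changes during one operation, does the score change with it?

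The objective is to back the surgeon's judgement with a number, and SAP 6.4.3 presents CEF as the numerical counterpart of that judgement. CEF is built from the two color contrasts that enter these correlations. The second question bears most directly on that use, and a pooled value cannot be read as an answer to it.

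Elsewhere the SAP does separate these levels. The first key secondary analysis averages time points within each participant before testing (SAP 6.4.2), and the BICR reliability analysis treats inter- and intra-rater agreement separately (SAP 6.4.4).

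**Working it through.** The plan states no target, expected value or interval for this correlation, so there is no figure of its own to reproduce. The check asks what the planned coefficient estimates.

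**Inputs.** From the documents: repeated pairs, varying in number, one ureter per participant, one pooled coefficient per mode. Assumed, because the documents do not give them: the ICC of contrast (ICCx) and of score (ICCy), meaning the share of variance that lies between participants; the between-participant correlation rB; the within-participant correlation rW; and the number of time points m.

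**Step 1: what the pooled coefficient is.** Split each variable into a participant part and a residual part. If the associations do not depend on m, then

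pooled r = rB × √(ICCx × ICCy) + rW × √((1 − ICCx)(1 − ICCy)).

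With a common ICC this reduces to rB × ICC + rW × (1 − ICC).

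**Step 2: two opposite truths.**

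| Common ICC | rB = 0.7, rW = 0 | rB = 0, rW = 0.7 |
|---|---|---|
| 0.3 | 0.7 × 0.3 = 0.21 | 0.7 × 0.7 = 0.49 |
| 0.5 | 0.7 × 0.5 = 0.35 | 0.7 × 0.5 = 0.35 |
| 0.7 | 0.7 × 0.7 = 0.49 | 0.7 × 0.3 = 0.21 |

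At ICC 0.5 the two situations cannot be told apart. Simulation with 1 to 8 time points per participant agrees (about 0.35 in both). Away from 0.5, the value depends on an ICC the reader will not have.

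**Step 3: when the pooling is harmless.** If rB = rW = 0.5 with a common ICC, pooled r = 0.5 × ICC + 0.5 × (1 − ICC) = 0.50.

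**Step 4: weighting.** Simulation with an assumed 93 participants (70 randomized adults at an assumed 5:1 allocation, 10 with moderate or severe impairment, 13 adolescents) gives the longest quarter of surgeries 26% of pairs if everyone has 4 time points, 42% if time points are uniform on 1 to 6, and 47% if they are skewed with median 4. This moves the estimate only if the association differs with surgery length. With a true correlation of 0.1 in the longest 31% of surgeries and 0.6 in the rest (skewed case), the pooled value is 0.33. Equal weight per participant gives 0.44 (0.69 × 0.6 + 0.31 × 0.1 ≈ 0.445).

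**Step 5: what separates the two parts.** Centring each participant's pairs recovers rW: 0 in the first column of Step 2 and 0.7 in the second. Correlating participant means does not fully isolate rB. With m time points each and a common ICC,

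r of means = (rB × ICC + rW × (1 − ICC)/m) / (ICC + (1 − ICC)/m).

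At ICC 0.5 and m = 4 this is 0.35/0.625 = 0.56 for the first truth and 0.0875/0.625 = 0.14 for the second, against true values of 0.7 and 0. The two cases are now clearly apart, but the means still carry some within-participant variation.

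**The case against.** The strongest reply is that this is a descriptive statistic for an additional secondary endpoint, and that it answers a plain image-level question: do images with more contrast get higher scores? That stands. The coefficient is not meaningless, and Step 3 shows a case where pooling costs nothing.

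Several stronger readings are tempting, and the documents do not support them:

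- **Inflated false-positive rate or false precision.** A reader might infer this because the pairs are not independent. The SAP plans no p-value, interval or threshold for this coefficient. For the adolescent and the moderate and severe impairment groups, SAP 6.4.3 says of the additional secondary endpoints: "P-values and confidence intervals will not be presented".
- **Long surgeries dominate.** The documents give no distribution of time points in advance; SAP 6.4.5 will report it afterwards. Under the assumptions in Step 4 the longest quarter holds less than half the pairs, and nothing in the documents suggests that the association varies with surgery length.
- **The coefficient is the sole support for the image measure.** SAP 6.4.3 also plans boxplots of CEF by conspicuity score and summaries of contrast and CEF by time point. No provision for repeated measures is stated for these either, but they are further evidence.
- **Camera gain drives the between-participant part.** Contrast is defined as a ratio inside versus outside the ureter, so a uniform gain cancels.

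What remains is that the point estimate itself is ambiguous, whether or not a test is attached.

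**Conclusion.** The concern holds as a matter of interpretation. For each mode, the planned coefficient weights participants by their number of time points and blends between- and within-participant association, so it cannot show that contrast follows the investigator's score within a participant. The size is illustrated by two opposite truths that both give 0.35. That figure rests on an assumed ICC of 0.5 for both variables and on deliberately extreme correlations (0.7 and 0). With similar between- and within-participant associations the loss is small or nil, but the planned output would not let a reader see which case applies. The primary and key secondary tests (H1 to H3) and the BICR concordance criterion are not affected. This is an inexpensive improvement to a supportive analysis and not a threat to the trial's conclusions.

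**What to change.** In SAP 6.4.3, for each illumination mode, replace or accompany the overall coefficient with:

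1. The Pearson coefficient at the 30-min time point, one pair per participant. This gives participants equal weight and removes the repetition, but does not by itself separate the two associations.
2. Over all time points, a within-participant coefficient (participant-centred, repeated-measures) and a between-participant coefficient. The latter should either be labelled as the correlation of participant means, with a note that it retains some within-participant variation, or be taken from a bivariate mixed model.

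If an interval is shown, obtain it from a bootstrap that resamples participants. In simulations at ICC 0.5 with the assumed 93 participants, a 95% interval that treated pairs as independent covered the true value only 75% to 87% of the time.

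The cost is SAP wording, a little programming and a few more coefficients to report; no new data are needed. Participants with one time point or constant scores will add little or nothing to the within-participant coefficient, so the number who do contribute should be stated beside it.
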